8.1.4 Adjustments for Covariates

Not applicable to this study.

8.1.5 Handling of Dropouts or Missing Data

Incomplete start and end dates for medications will be imputed. Incomplete start dates for adverse events (AEs) will be imputed. Other data will not be imputed and will be summarized on an observed case basis.

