5.2. Study Flow Chart for patients entered from Study SGT-54-01 or SGT-54-02

Procedure	Visit 2 ^{1,2,7}	Visit 3, 4, 6, 7, 9, 10	Visit 5, 8, 11	Visit 12 (EOT ³ /EOS ⁴)	Unscheduled Visit ¹¹
Name of Visit	Baseline Day 1	Week 4, 8, 16, 20, 28, 32 ⁵ Day 29, 57, 113, 141, 197, 225	Week 12, 24, 36 ⁵ Day 85, 169, 253	Week 40 Day 281 ⁶	
Visit window		± 10 days	± 10 days	± 10 days	
Entry Criteria	X				
Sign Informed Consent	X				
Demographics	X				
Medical History/Previous Therapies	X				
Con med	X	X	X	X	X
Pregnancy Test ⁷	X	X	X	X	X
Brief Physical Examination	X		X	X	X
Cutaneous Safety Assessment and Local Tolerability Assessments	X	X	X	X	X
Administer/ Review Patient Instructions	X	X	X		X
IGA ⁸	X	X	X	X	X
Rosacea Erythema Assessment	X	X	X	X	X
Telangiectasia Assessment	X	X	X	X	X
Weigh Study Product	X	X	X	X	X
Study Product Dispensed ⁹	X	X	X		X
Provide Cleanser and Moisturizer/Sunscreen, if needed	X	X	X		X
Study Product Collected		X	X	X	
Diary Card dispensed	X	X	X		X
Diary Card collected		X	X	X	X
Adverse Events	X	X	X	X	X
Complete RosaQoL ¹⁰	X		X	X	

¹ Patient will be eligible for the extension study only after completing 12 weeks of one of the two Phase 3 studies SGT-54-01 or SGT-54-02 at the Week 12 window time (± 4 days) and missed not more than one visit of Visits 3, 4 or 5 in these studies.

² Same Visit as Visit 6 in Phase 3 Study SGT-54-01 or Study SGT-54-02. All procedures that were performed in Visit 6 of Study SGT-54-01 or Study SGT-54-02 will be captured in the Study SGT-54-07 source document.

³ EOT – end of treatment.

⁴ EOS – end of study.

⁵ All visits must be in reference to baseline and counted accordingly.

⁶ All Week 40 procedures should be completed for Patients who terminate early.

⁷ Urine test for women of childbearing potential.

⁸ For product dispensing eligibility

⁹ The dispensation and usage of the pump is based on IGA score.

¹⁰ RosaQoL is a Rosacea Quality of Life questionnaire

¹¹ Perform procedures per PI discretion.

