13.2. Screen Failure and Discontinuation Criteria

For new patients, a screen failure is a patient who is not randomized/enrolled in the study due to ineligibility, after signing an Informed Consent Form, and did not receive study product. The Informed Consent Form signed by the patient should be kept with the source document for patients who do not pass the screening procedures. The documentation should include identification of the eligibility criterion or criteria that were and were not met. The patient should not be re-screened for this study without Sol-Gel's approval.

Although encouraged to complete the study whenever possible, patients are free to discontinue their participation in this study at any time and for any reason without prejudice. A patient may be withdrawn from the study prior to study completion for any of the following reasons:

- Investigator opinion that it is not in the patient's best interest to continue.
- Patient Request /Withdraw Consent – Whenever the patient decides it is in his/her best interest to withdraw.
- Adverse Event – when the investigator thinks it's in the patient's best interest
- Lost to Follow-up – Documentation confirmed at minimum by two phone calls and certified letter. Best effort should be performed to capture an explanation for the lost-to follow-up event.
- Protocol Violation – When requirements of the protocol are not respected, especially when patient safety is concerned.
- Pregnancy
- Worsening of condition that requires alternate therapy.

In the event that the Sponsor terminates the study early, every effort will be made to allow patients to complete at least 6 months of treatment.

In the case of patients who discontinue due to an Adverse Event, the Investigator will conduct follow-up contacts with the patient until the Investigator, Sponsor and Medical Monitor agree the event is satisfactorily resolved and/or stabilized.

Patients discontinued early from the study shall not be replaced.

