7. EFFICACY AND SAFETY ENDPOINTS

7.1 Efficacy Endpoints

This study is not intended to assess efficacy.

IGA is included to determine the need for treatment and subsequent re-treatment after treatment course (in either Study SGT-54-01 or Study SGT-54-02) and any subsequent 4-week courses, if applicable. Certain efficacy data and endpoints will, however, be summarized.

The number of retreatments and the number of treatment free days until the first retreatment (relapse) will be calculated as described in Section [8.7.2.2](#).

RosaQoL will be completed at Baseline, Visits 5, 8, 11, 14, and End of Study. The RosaQoL data of patients who were enrolled from SGT-54-01 or SGT-54-02, will be used from the questionnaire completed at Visit 6/Week 12 of SGT-54-01 or SGT-54-02.

Erythema severity and telangiectasia assessments will be completed at each study visit.

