8. STATISTICAL AND ANALYTICAL PLANS

8.1 General Methodology

All statistical processing will be performed using SAS® version 9.4 or later unless otherwise stated.

Descriptive statistics will be used to provide an overview of the efficacy and safety results. For categorical parameters, the number and percentage of subjects in each category will be presented. For continuous parameters, descriptive statistics will include n (number of subjects), mean, standard deviation (SD), median, minimum (min) and maximum (max).

No inferential testing or imputations for missing data will be performed. No interim analyses are planned.

All analyses will be performed using the Safety Population of the study.

Where applicable the analysis will be presented by overall treatment group in 54-07 as well as by treatment group assignment in 54-01/54-02.

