8.8.1 IGA

Descriptive statistics will be used to summarize the assessment of efficacy. IGA scores will be summarized at Baseline (see definition of baseline in Section 8.1.2) and every 4 weeks through end of the study. The number and percentage of patients who achieve treatment success at the scheduled study visits will be tabulated. A patient will be considered a success if their IGA score is clear or almost clear.

In addition to the above summary a by-subject listing of all IGA results will be presented.

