8.8.2.1 RosaQoL

The mean change in RosaQoL subscale scores from Baseline to Weeks 12, 24, 36, 48 and 52 will be summarized using descriptive statistics.

The subscores for the RosaQoL are computed as follows:

Total Score: the unweighted mean of all RosaQoL questions

Symptom subscale score: the unweighted mean of the following symptom questions

My rosacea burns or stings (item #2)

My rosacea is irritated (item #6)

My rosacea makes my skin sensitive (item #9)

My skin feels bumpy (uneven, not smooth, irregular) (item #16)

My skin flushes (item #17)

My skin gets irritated easily (cosmetics, aftershaves, cleansers) (item #18)

My eyes bother me (feels dry or gritty) (item #19)

Functional subscale score: the unweighted mean of the following functional questions

I try to cover up my rosacea (with make-up) (item #13)

I avoid certain foods or drinks because of my rosacea (item #15)

I avoid certain environments (heat, humidity, cold) because of my rosacea (item #21)

Emotion subscale score: the unweighted mean of the following emotion questions

- I worry that my rosacea may be serious (item #1)
- I worry about getting scars from my rosacea (item #3)
- I worry that my rosacea may get worse (item #4)
- I worry about side effects from rosacea medications (item #5)
- I am embarrassed by my rosacea (item #7)
- I am frustrated by my rosacea (item #8)
- I am annoyed by my rosacea (item #10)
- I am bothered by the appearance of my skin (redness, blotchiness) (item #11)
- My rosacea makes me feel self-conscious (item #12)
- I am bothered by persistence/reoccurrence of my rosacea (item #14)
- I think about my rosacea (item #20)

Each individual item should be scored as follows: 1=Never, 2=Rarely, 3=Sometimes, 4=Often, and 5=All the time. Missing data values will not be used. If a subscale has items with missing results, the subscore and the total will not be calculated.

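### By-visit IGA success uses observed cases, so patients withdrawn for lack of efficacy or worsening drop out of later rows and late-visit success can be overstated (minor)

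*SAP*

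**What the plan says.** **Success measure.** SAP 8.8.1: "The number and percentage of patients who achieve treatment success at the scheduled study visits will be tabulated", with the definition "A patient will be considered a success if their IGA score is clear or almost clear". Table 14.2.1.2 prints Success and Failure rows from Week 4 to Week 52 for the Safety Population.

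**Missing data.** SAP 8.1: "No inferential testing or imputations for missing data will be performed". SAP 8.1.5, after allowing imputation of some medication and adverse-event dates: "Other data will not be imputed and will be summarized on an observed case basis".

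**Withdrawal.** Protocol 13.2 lists among the reasons for which a patient may be withdrawn: "Worsening of condition that requires alternate therapy". The disposition shell (Table 14.0.1) has separate rows for lack of efficacy and for worsening of condition. No text links either reason to the success rows.

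**Early termination.** Protocol 5.2, footnote to the flow chart: "All Week 40 procedures should be completed for Patients who terminate early". Those procedures include the IGA. SAP 8.1.3 assigns an ET value to one visit by study-day window. It excludes ET values before study day 22, and ET values whose mapped visit already has a scheduled result.

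**End-of-study table.** Table 14.2.1.1 summarises IGA success at the nominal 54-07 visit Week 40/ET.

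**Role of efficacy.** SAP 7.1: "This study is not intended to assess efficacy". Selected efficacy data are nevertheless summarised.

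**The concern.** For these two withdrawal reasons, the cause of the missing value is the outcome being tabulated. A patient who leaves because the rosacea is not controlled stops contributing to Table 14.2.1.2, while a patient who does well stays in it. Each by-visit percentage therefore describes success among patients still attending.

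Such leavers accumulate, so the gap tends to be widest at the late visits, and durability over 52 weeks is what a reader will look for in this table. A success percentage that rises with time could partly reflect who is left.

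**Working it through.** **Plan's own figure.** There is none to reproduce. The documents state no expected success rate, withdrawal rate or dropout allowance. SAP 9 says only that the sample size follows the minimum requirement for a long-term safety study.

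**Step 1: where an ET failure goes.** The windows in SAP 8.1.3 assign study days 43–70 to 54-07 Week 8 (target day 57) and days 71–98 to Week 12 (target day 85). Take a patient seen on schedule at day 57 who then leaves for worsening.

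| ET day (illustrative) | Maps to 54-07 visit | Result in Table 14.2.1.2 | Analysis visits with no value afterwards |
|---|---|---|---|
| 65 | Week 8, scheduled value present | ET value discarded | Former E-BPO: Weeks 24–52 (8 rows). Former vehicle: Weeks 12–40 (8 rows) |
| 80 | Week 12, no scheduled value | Counts once | Former E-BPO: Weeks 28–52 (7 rows). Former vehicle: Weeks 16–40 (7 rows) |

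The analysis visits come from the mapping table in SAP 8.1.3. It places 54-07 Week 8 at analysis Week 20 and 54-07 Week 12 at analysis Week 24 for patients who had active cream in the parent study.

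**Step 2: size of the gap.** Let n be the patients observed at a visit and p the observed success proportion. Let k be the patients withdrawn earlier for lack of efficacy or worsening, and w = k/(n + k). Then:

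- observed-case success = p
- success with these withdrawals counted as failures = pn/(n + k) = p(1 − w)
- gap = p × w

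Both p and w are assumptions.

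| w | p = 40% | p = 60% | p = 80% |
|---|---|---|---|
| 2% | 0.8 points | 1.2 points | 1.6 points |
| 5% | 2.0 points | 3.0 points | 4.0 points |
| 10% | 4.0 points | 6.0 points | 8.0 points |

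**Step 3: why the denominator of a fix matters.** Assume 700 patients, observed success 60%, 5% (35) withdrawn for these two reasons, and 20% (140) missing for any other reason. Observed: 700 − 35 − 140 = 525, with 0.60 × 525 = 315 successes.

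- Observed cases: 315/525 = 60.0%
- Only the two failure-related reasons counted as failures: 315/(525 + 35) = 315/560 = 56.25%
- Every missing patient counted as a failure: 315/700 = 45.0%

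The middle row moves the figure by 3.75 points, which equals p × w with w = 35/560 = 6.25%. The last row moves it by 15 points, mostly through patients whose absence says nothing about failure.

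**Step 4: direction for missing data in general.** With 25% missing and 60% observed success, the full-cohort rate is 0.75 × 60% + 0.25 × q, where q is the success rate among the missing. For q = 0%, 30%, 60% and 90% this gives 45.0%, 52.5%, 60.0% and 67.5%. The upward direction is fixed only for the failure-related withdrawals, and only relative to counting them as failures.

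**The case against.** The strongest reply is about weight. Efficacy is not an objective, the IGA serves to decide dispensing, and nothing is tested, so no formal conclusion rests on these rows. Both documents rule out imputation openly, and the shell prints n at every visit beside the column N, so the shrinking sample is visible. Early terminators have an IGA, SAP 8.1.3 maps it into the by-visit table, and Table 14.2.1.1 keeps it in the Week 40/ET result.

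Most of this stands, and it is why the point is minor. It does not remove the gap. The ET value fills at most one row. Table 14.2.1.1 does keep leavers with an ET IGA, but it pools Week 40 with terminations at any time. Its nominal Week 40 is also analysis Week 40 for former vehicle patients and Week 52 for former E-BPO patients. It cannot correct success at a stated duration. A printed n shows that patients are missing, not why.

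Three stronger readings are tempting but not supported:

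- **That these leavers never count as failures.** The ET mapping lets some of them count once.
- **That enrolling about 700 with minima of 300 at 28 weeks and 100 at 52 weeks implies an allowance for losing 400 patients.** Those minima are follow-up targets and the point at which the sponsor may stop. They are not a dropout assumption.
- **That all missing patients should be failures.** Steps 3 and 4 show that this could introduce a larger distortion than the one it removes.

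**Conclusion.** The point holds as a minor one. After withdrawal for lack of efficacy or worsening, a patient can appear as a failure in Table 14.2.1.2 at most once more and is then absent from every later row. Late-visit success can therefore be higher than it would be with these patients counted as failures.

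The size cannot be determined from the documents. For p between 40% and 80% it is about 1 point (0.8 to 1.6) if such withdrawals are 2% of observed plus withdrawn, and 4 to 8 points if they are 10%.

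This rests on treating withdrawal for these reasons as failure at all later visits. That is a reasonable convention, but the plan does not state it: Protocol 13.2 permits such withdrawal without requiring it, and does not define worsening by IGA grade. A reader might infer that long-term success is in fact overstated. The documents do not show that, because few or no patients may have left for these reasons. No inferential conclusion changes either way.

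**What to change.** In SAP 8.8.1 and Table 14.2.1.2:

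1. Keep the observed-case rows and state that their percentages use n at the visit. The shell does not say whether the denominator is n or N.
2. Add one supplementary success row per visit. Its denominator is the patients observed at that visit plus those withdrawn earlier for lack of efficacy or worsening of condition, with the latter counted as failures.
3. Print the cumulative number withdrawn for these two reasons beside the row.
4. Do not count any of the following as failures: sponsor termination, loss to follow-up, withdrawal by subject, pregnancy, adverse-event withdrawals, missed visits, or weeks not scheduled for the cohort (former vehicle patients after Week 40).
5. Record the row as a stated exception to the no-imputation sentence, for example in SAP 10.

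The cost is some SAP and shell wording and one programmed row per visit, from disposition reasons already collected. SAP 2 allows updates until database lock. The downside is a longer table and slightly lower late-visit percentages in the added row. If few patients left for these reasons, the row will show that the observed-case figures are sound.

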8.1.5.1 Medication Date Imputation

If the medication or procedure/therapy start date is incomplete, then it will be imputed as follows for the purpose of determining concomitant use:

- If the start date is completely missing, the start date will be equal to the first dose date. However, if the stop date is not missing and is before the first dose date, then the stop date will be used instead.
- If the start day is missing, the first day of the month will be used.
- If the start day and month are missing, then the first day of the first month (January) will be used.

If the medication or procedure/therapy stop date is incomplete, then it will be imputed as follows for the purpose of determining concomitant use:

- If the stop date is completely missing and the medication is not ongoing, the stop date will be equal to the last dose date or date of completion/withdrawal, whichever is the latest.
- If the stop day is missing, the last day of the month will be used.
- If the stop day and month are missing, then the last day of the last month (December) will be used.

8.1.5.2 Adverse Event Start Date Imputation

If the AE start date is incomplete, then it will be imputed as follows for the purpose of determining study day for the AE period breakdown described in Section 8.8.2:

- If the start date is completely missing, the start date will be equal to the first dose date. However, if the stop date is not missing and is before the first dose date, then the stop date will be used instead.
- If the start day is missing, the first day of the month will be used.
- If the start day and month are missing, then the first day of the first month (January) will be used.

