8.9.2 Adverse Events

AEs from 54-01/02 will be included in the analysis for 54-07. All AEs that were reported as ongoing in 54-01/02 will be added into the CRF for 54-07, while AEs reported as recovered/resolved will be pulled forward programmatically into 54-07.

AEs occurring during the study will be recorded and classified on the basis of MedDRA terminology. Descriptions of AEs will include the date of onset, the date the AE ended, the severity of the AE, the relationship to study product, the action taken regarding study product usage, the action taken to treat the AE, and the outcome. All reported treatment-emergent AEs (TEAEs) will be summarized by the number of patients reporting AEs, system organ class, severity, seriousness, and relationship to study product. TEAEs are those AEs with an onset on or after the date of the first study product application. For AEs recorded in the 54-07 study if the AE is not indicated as prior to first application on the CRF then it will be considered a TEAE. AEs from 54-01/02 for subjects who received S5G4T-1 in 54-01 or 54-02 will be considered a TEAE if they were considered at TEAE in the 54-01/02 study. AEs (including ongoing) from 54-01/02 study for subjects who received vehicle in 54-01 or 54-02 will be considered pre-treatment.

AEs will be summarized by period (and total) and by severity. Each patient will be counted only once within a SOC or a Preferred Term by using the AEs with the highest severity within each category.

AEs will be summarized by period (and total) and by relationship to study product. Each patient will be counted only once within a system organ class or a preferred term by using the AEs with the greatest relationship within each category.

If relationship to study drug is reported as definitely, probably, or possible, then this is defined as related. If relationship to study drug is reported as unlikely or not related, then this is defined as unrelated.

TEAEs will be summarized in total as well as by the following periods based on time of onset in relation to date of first application of S5G4T-1, based on the definitions below. Start dates will be imputed as described in Section 8.1.5.2.

- 0-12 Weeks $0 \leq \text{onset day} \leq 85$
- >12-28 Weeks $86 \leq \text{onset day} \leq 197$
- >28-52 Weeks $198 \leq \text{onset day} \leq 365$
- >52 Weeks $\text{onset day} \geq 366$

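### Partial adverse event start dates are imputed with no floor at first S5G4T-1 application, so some treatment-emergent events fall into no period of the by-period tables

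*SAP*

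**What the plan says.** **Imputation (SAP 8.1.5.2).** AE start dates are imputed "for the purpose of determining study day for the AE period breakdown described in Section 8.8.2". There are three rules:
- Day missing: "If the start day is missing, the first day of the month will be used".
- Day and month missing: "If the start day and month are missing, then the first day of the first month (January) will be used".
- Whole date missing: "If the start date is completely missing, the start date will be equal to the first dose date", unless a known stop date precedes first dose. This is the only rule that mentions first dose.

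**TEAE status (SAP 8.9.2).** Status does not depend on the imputed date. For AEs recorded in SGT-54-07, "if the AE is not indicated as prior to first application on the CRF then it will be considered a TEAE". AEs from the parent trials in subjects who received S5G4T-1 there "will be considered a TEAE if they were considered at TEAE in the 54-01/02 study". Parent-trial AEs of vehicle subjects are pre-treatment.

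**Periods (SAP 8.9.2).** TEAEs are assigned to periods "based on time of onset in relation to date of first application of S5G4T-1, based on the definitions below", using the imputed dates. The periods cover onset days 0 to 85, 86 to 197, 198 to 365, and 366 onwards. The AE listing footnotes compute the day of a date before first application as that date minus the first application date, which is negative.

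**The concern.** An event can be a TEAE by its flag and still carry an imputed start date before first application. The period definitions have no place for it, and neither document supplies a floor or a default period.

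Imputing AE dates early is normally defended because it keeps doubtful events in the treatment-emergent set. Here the flag or parent-study status has already done that, so imputing before first application protects nothing and only removes the event from the period tables.

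Protocol 18.4 asks for safety data by period. The SAP plans eight such tables: 14.3.1.3.1 to 14.3.1.3.4 for TEAEs and 14.3.1.5.1 to 14.3.1.5.4 for serious TEAEs. A TEAE counted overall but in no period column would be a visible discrepancy, most of all if it were serious.

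**Working it through.** **1. Period bounds.** With day 1 as the day of first application, the end of week w is day 7w + 1: 7×12 + 1 = 85, 7×28 + 1 = 197, 7×52 + 1 = 365. These match SAP 8.9.2.

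**2. Applying the rules.** Onset day = date − first application if earlier, otherwise that difference + 1. The illustration assumes first application on 17 September 2018.

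| Recorded start | Imputed | Day as planned | Period | Day with floor | Period |
|---|---|---|---|---|---|
| Sep 2018 | 1 Sep 2018 | −16 | none | 1 | 0-12 Weeks |
| 2018 | 1 Jan 2018 | −259 | none | 1 | 0-12 Weeks |
| Oct 2018 | 1 Oct 2018 | 15 | 0-12 Weeks | 15 | 0-12 Weeks |
| 2019 | 1 Jan 2019 | 107 | >12-28 Weeks | 107 | >12-28 Weeks |

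Only partial dates in the month (day missing) or year (day and month missing) of first application go negative. A same-month date does so for 365 − 12 = 353 of 365 possible first-application dates, and a same-year date for 364 of 365.

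**3. Share lost, day missing.** Assumptions: first applications spread evenly over a 365-day year, and true onset uniform over H days. If first application falls on day j of a month of length L (j ≥ 2), the L − j + 1 onset days left in that month are lost. Summing over j gives L(L − 1)/2 per month. Over the year this is 7×465 + 4×435 + 378 = 5,373. The share is 5,373/(365×H):
- H = 85: 5,373/31,025 = 17.3%
- H = 281: 5,373/102,565 = 5.2%
- H = 365: 5,373/133,225 = 4.0%

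**4. Share lost, day and month missing.** The same reasoning by year gives 88.2%, 61.4% and 49.9% for H = 85, 281 and 365. For H = 365, for example, (364×365/2)/133,225 = 66,430/133,225 = 49.9%.

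**5. Who is exposed.** S5G4T-1 rollovers enter SGT-54-07 at about day 85 ± 4, that is days 81 to 89. A day-missing date moves back at most 30 days, so an AE starting in SGT-54-07 is imputed no earlier than about day 81 − 30 = 51. The day-missing loss therefore concerns vehicle rollovers early in SGT-54-07 and parent-trial AEs of S5G4T-1 subjects. SAP 10 confirms that nobody else was enrolled.

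**6. Effect on the tables.** The event remains in Tables 14.3.1.2.x (and 14.3.1.4.x if serious) and in the listings, so the event-count rows of the period tables sum to less than the overall count. Each period's denominator counts subjects who complete it plus those with an AE in it. A subject who leaves before week 12, and whose only AE in that period is lost, drops out of both numerator and denominator of 0-12 Weeks.

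**7. Completely missing dates.** Reading first dose as first S5G4T-1 application, an AE new in SGT-54-07 in an S5G4T-1 rollover is placed on day 1 of the parent trial, about 12 weeks before SGT-54-07 entry.

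**The case against.** The best counter-argument is that few dates will be affected. Protocol 13.13 and 13.14 ask about AEs since the previous visit roughly every four weeks. Onset date is a required AE descriptor, and serious AEs must be reported within 24 hours with supporting documentation. A year-only date collected this way is unlikely. Dates brought forward from the parent trials may already be complete; those datasets are not available here. This stands, and it limits the likely size. It does not supply the missing rule.

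Four stronger readings are tempting, and the documents do not support them:
- A reader might infer that every partial date drops out. Only those in the month or year of first application do.
- A reader might infer that TEAEs are lost from the study's totals. They are not. Nor should subject counts be expected to add across periods, since one subject can appear in several; only the event-count rows should reconcile.
- A reader might infer that late-exposure rates are understated. Under the assumptions above, about 10% (281 days) or 8% (365 days) of day-missing TEAEs do land in an earlier period. That follows from any first-of-month convention, the proposed floor leaves it unchanged, and without a count of partial dates no material bias can be claimed.
- A reader might assume front-loaded onset and reach a larger share. An exponential onset with mean 21 days gives about 46% of 0-12 week day-missing TEAEs. The documents give no onset distribution, so that figure should not be relied on.

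**Conclusion.** The gap is real and narrow. As written, SAP 8.1.5.2 and 8.9.2 together exclude certain TEAEs from all by-period tables while keeping them in the overall tables. The 0-12 Weeks event count, and sometimes its denominator, can be too low.

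The 17% (first 85 days) and 4 to 5% (281 to 365 days) rest on evenly spread first-application dates and uniform onset. They are shares of day-missing TEAEs, not of all TEAEs. The absolute effect is unknown and may be small. The point is worth settling before database lock because the rule is stated, nothing else in the plan repairs it, and the repair is nearly free.

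**What to change.** Amend SAP 8.1.5.2 as follows:

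1. For any AE classed as a TEAE, take the later of the imputed start date and the date of first S5G4T-1 application, never past a known stop date.
2. For AEs with onset in SGT-54-07, also apply the SGT-54-07 Baseline date as a floor, again never past a known stop date. Exclude AEs that were ongoing from SGT-54-01/02 and re-entered in the SGT-54-07 CRF (SAP 8.9.2); their onset lies in the parent trial and the floor would move them too late.
3. Correct the cross-reference from Section 8.8.2, which is Retreatments, to Section 8.9.2.

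One limit of item 2: for S5G4T-1 rollovers, Baseline falls on about days 81 to 89, and day 85 is still in 0-12 Weeks. The floor corrects the onset day, but on its own it moves an event to the next column only when Baseline is day 86 or later. The SAP should state that this is accepted.

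The cost is a few sentences and a small programming change, plus a match of SGT-54-07 AEs to ongoing parent-trial records for item 2. The SAP Preface allows updates until database lock.

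### Partial AE start dates are imputed with no floor at first S5G4T-1 application, so a TEAE dated only to the first-dose month (or year) falls in no by-period column

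*SAP*

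**What the plan says.** SAP 8.1.5.2 has three rules for incomplete AE start dates.

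- Day missing: "If the start day is missing, the first day of the month will be used".
- Day and month missing: "If the start day and month are missing, then the first day of the first month (January) will be used".
- Date wholly missing: "If the start date is completely missing, the start date will be equal to the first dose date", unless a known stop date is earlier, in which case the stop date is used.

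Only the third rule refers to first dose. The section limits what the imputed date is for: it is "imputed as follows for the purpose of determining study day for the AE period breakdown described in Section 8.8.2". (SAP 8.8.2 is Retreatments; the AE periods are in 8.9.2.)

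SAP 8.9.2 decides treatment emergence without the imputed date. For AEs recorded in 54-07, "if the AE is not indicated as prior to first application on the CRF then it will be considered a TEAE". AEs from the parent studies in subjects who received S5G4T-1 there "will be considered a TEAE if they were considered at TEAE in the 54-01/02 study". The same section then promises that "TEAEs will be summarized in total as well as by the following periods based on time of onset in relation to date of first application", counted from the first S5G4T-1 dose. The periods are onset days 0 to 85, 86 to 197, 198 to 365, and 366 onward. The by-period table shells have those four columns and no place for an unassigned event.

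**The concern.** Classification and timing come from different sources. An event can be a confirmed TEAE by flag and still carry an imputed start date before the first dose. The period scheme has no slot for a negative onset day, so the event stays in the TEAE total and disappears from the by-period tables.

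Those tables are where this long-term safety study shows how AE frequency changes with time on product, and the serious-AE period tables use the same rule. There is a second effect. The footnotes define each period's denominator as subjects who complete the period or have an AE in it. An unassigned AE can therefore also remove a non-completer from the denominator, for example a former vehicle subject who stops early in 54-07.

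**Working it through.** The plan states no figure on this point, so the check applies its rules literally.

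**Inputs**
- Imputation rules: SAP 8.1.5.2.
- Day formula, from the AE listing footnotes: before first application, day = date - first application date; on or after it, day = date - first application date + 1.
- Periods: SAP 8.9.2.

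**Worked record** (illustrative dates: first S5G4T-1 dose 17 Sep 2018, true onset on day 8)
- Recorded as Sep 2018: imputed to 1 Sep; day = 1 - 17 = -16; no period.
- Recorded as 2018: imputed to 1 Jan; day = -259; no period.

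**How general this is** (every first-dose date in a 365-day year)
- Month-only, AE in the first-dose month: the day is negative for 365 - 12 = 353 of 365 dates (96.7%), that is, all but the 1sts. The range is -1 to -30.
- Year-only, AE in the first-dose year: negative for 364 of 365 dates (99.7%), down to -364.

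**Share of partially dated TEAEs lost** (assumed, not from the documents: first dose uniform over the year, onset uniform over D days)

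Month-only. In a month of L days, the lost onset days summed over first-dose dates are L(L-1)/2. Over the year this is 7 × 465 + 4 × 435 + 378 = 5,373, or 5,373/365 = 14.72 days per subject. Divide by D.

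Year-only. The lost onset days summed over first-dose dates are the sum of min(D, n) for n = 1 to 364. Divide by 365 for days per subject, then by D.

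| D (days) | Month-only: days lost | Month-only: share | Year-only: days lost | Year-only: share |
|---|---|---|---|---|
| 85 | 14.72 | 17.3% | 27,370/365 = 74.99 | 88.2% |
| 281 | 14.72 | 5.2% | 62,944/365 = 172.45 | 61.4% |
| 365 | 14.72 | 4.0% | 66,430/365 = 182.0 | 49.9% |

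The D = 85 row is the loss among events truly in weeks 0-12.

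**Which periods lose events**
- Month-only: a lost event starts within the first-dose month, at most 30 days after first dose. All such losses are therefore truly in weeks 0-12.
- Year-only: weeks 0-12 account for 74.99/172.45 = 43% (D = 281) or 74.99/182.0 = 41% (D = 365). The remaining 57-59% belong to later periods.

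**Early clustering.** In a simulation where half of AEs have exponential onset with mean 21 days (assumed), about 25% of all month-only TEAEs are lost, and about 40% of those truly in weeks 0-12. Of the year-only losses, 21-23% then belong to later periods.

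**Effect on the 0-12 week column.** If 2-10% of AEs lack only the day (assumed), the loss runs from 0.02 × 0.173 = 0.3% to 0.10 × 0.40 = 4% of its events.

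**With a floor at first application**, no partially dated TEAE is left without a period. Month-only events in the first-dose month go to day 1, in the correct 0-12 week column. Year-only events also go to day 1, which may be wrong: with first dose on 15 March and true onset on 25 October (day 225, >28-52 weeks), the floored date lands in weeks 0-12.

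**The case against.** The strongest reply is that this is a small programming gap. AEs are asked about at four-weekly visits and onset date is a required descriptor, so partial dates, and year-only dates above all, should be uncommon. The overall tables (14.3.1.2.x, and 14.3.1.4.x for serious TEAEs) keep every event, and the TEAE listing shows each one with its start date and day. No inferential testing is planned. The by-period counts by system organ class and preferred term count subjects once per period, so they would not sum to the overall counts anyway. Strict reconciliation concerns only the event-count rows of Tables 14.3.1.3.1 and 14.3.1.5.1. All of this stands and limits the size of the point, but none of it gives the affected events a column.

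Three stronger readings are tempting, and the documents do not support them.

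- *Early local irritation would be understated.* Protocol 15.1 and 15.2 keep dryness, scaling, itching and burning/stinging out of AE reporting unless they lead to interruption, discontinuation or new medication. The visit scores go to Table 14.3.1.1, which AE dates do not affect.
- *The losses fall almost wholly in weeks 0-12.* That is true for month-only dates only.
- *The wholly-missing rule shows that the authors meant every TEAE to start at or after first dose.* That rule itself allows an earlier stop date to be used, and its wording matches the medication rule in SAP 8.1.5.1. It does not show intent for TEAEs specifically.

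**Conclusion.** The rule as written gives a wrong result for an identifiable type of record. A TEAE dated only to the month of first S5G4T-1 application falls in no period column unless that application was on the 1st. A TEAE dated only to the year of first application does so unless it was on 1 January. Nothing elsewhere in the protocol or SAP repairs this.

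The damage is confined to Tables 14.3.1.3.x and 14.3.1.5.x and their denominators. A reader might infer that events lose TEAE status or drop out of overall incidence. They do not, because status rests on the CRF flag or the parent-study classification.

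The size is unknown, because the documents do not give the share of partial dates. The 0.3-4% range for the 0-12 week column depends on an assumed 2-10% of AEs lacking only the day and on the assumed onset patterns. The high year-only percentages describe a record type that should be rare, and no prevalence is available for it. For subjects treated with S5G4T-1 in the parent studies, the week 0-12 events come from 54-01/54-02, whose date handling cannot be seen here. The overall effect is probably small, but it is avoidable and worth correcting before database lock.

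**What to change.** Add to SAP 8.1.5.2:

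> For an AE classed as treatment-emergent with the start day missing, if the reported month is the month of first S5G4T-1 application, the start date is set to the later of the imputed date and the date of first S5G4T-1 application, but not later than a known complete AE stop date.

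For year-only TEAEs in the first-dose year, do not treat the onset as early. Show them in an onset-period-unknown row or a footnote of the by-period tables. If the same floor is applied instead, footnote that the true period is unknown. Correct the cross-reference in 8.1.5.2 from 8.8.2 to 8.9.2.

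The cost is a sentence of SAP text, a line of code and one row or footnote in the shells; SAP section 2 allows updates before database lock. The 0-12 week AE percentage becomes slightly higher. If the floor is used for year-only dates, some later events will be shown as early: under the assumptions above, 57-59% of the recovered year-only events with uniform onset, or 21-23% with early clustering. That is why the separate display is preferable.
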